### 5.6.2 Adverse Events

All reported AEs will be classified by system organ class (SOC), preferred term and lower level term using Version 17.1 of MedDRA.

Summaries will be presented by treatment group as well as SOC and preferred term.

A treatment emergent AE (TEAE) is defined as an AE with a start date on or after the first dose of IMP. If an AE has a partial start date and it is unclear from the partial date (or the stop date) whether the AE started prior to or post first dose of IMP then the AE will be considered treatment emergent. If the start date of the AE is the same as the date of first dose of IMP and the plausible relationship to IMP is marked on the CRF as “Prior to study medication” then the AE will not be considered treatment emergent.

An AE will be considered treatment-related if the plausibility relationship to IMP is recorded on the CRF as ‘yes’. If the data on plausibility relationship to IMP is missing then the AE will be considered treatment-related.

An AE will be considered leading to permanent discontinuation of IMP if the action taken with IMP is recorded on the CRF as ‘study medication stopped’ or the outcome is recorded on the CRF as ‘patient died’.

An AE will be considered leading to IMP dose reduction excluding permanent discontinuation if the action taken with IMP is recorded on the CRF as ‘dose reduced’, ‘dose reduced temporarily’ or ‘study medication interrupted’.

An AE will be considered leading to temporary IMP dose reduction if the action taken with IMP is recorded on the CRF as ‘dose reduced temporarily’.

An AE will be considered leading to permanent IMP dose reduction excluding permanent discontinuation if the action taken with IMP is recorded on the CRF as ‘dose reduced’.

An AE will be considered fatal if the outcome is recorded on the CRF as ‘patient died’.

The following summaries will be generated (counts are by patient unless specified otherwise):

- Overall summary of AEs, including number of patients reporting each of; TEAEs, treatment-related TEAEs, TEAEs leading to withdrawal, treatment-related TEAEs leading to withdrawal, serious TEAEs, treatment-related serious TEAEs.
- Summary of TEAEs.
- Summary of TEAEs by event.
- Summary of treatment-related TEAEs.
- Summary of treatment-related TEAEs by event
- Summary of TEAEs by maximal severity.
- Summary of TEAEs by sex.
- Summary of serious TEAEs.
- Summary of serious TEAEs by event.
- Summary of non-serious TEAEs.
- Summary of non-serious TEAEs by event.
- Summary of treatment-related serious TEAEs.
- Summary of treatment-related serious TEAEs by event.
- Summary of TEAEs leading to permanent discontinuation of IMP.
- Summary of treatment-related TEAEs leading to permanent discontinuation of IMP.
- Summary of TEAEs leading to IMP dose reduction excluding permanent discontinuation (by resolution and overall).
- Summary of treatment-related TEAEs leading to IMP dose reduction excluding permanent discontinuation (by resolution and overall).
- Summary of TEAEs leading to temporary IMP dose reduction (by resolution and overall).
- Summary of treatment-related TEAEs leading to temporary IMP dose reduction (by resolution and overall).
- Summary of TEAEs leading to permanent IMP dose reduction excluding permanent discontinuation (by resolution and overall).
- Summary of treatment-related TEAEs leading to permanent IMP dose reduction excluding permanent discontinuation (by resolution and overall).
- Summary of fatal TEAEs.
- Summary of TEAEs by time of first onset of AE.
- Summary of TEAEs by time to AE resolution.
- Summary of TEAEs reported in  $\geq 2\%$  of patients (after rounding) in the GWP42003-P treatment groups and where the incidence is greater than the placebo treatment group.
- List of patients experiencing TEAEs by SOC and preferred term.
- Summary of pre-treatment AEs.

For the summary of TEAEs by maximal severity, for each patient, the worst severity recorded by preferred term, SOC and overall will be used for summary purposes. If severity is missing, the worst case (severe) will be assumed.

For summaries by resolution, AEs with an outcome of 'recovered' or 'recovered with sequelae' will be summarized as 'Resolved' and AEs with an outcome of 'continuing', 'patient died' or those with a missing outcome will be summarized as 'Not resolved'.

For the summary of TEAEs by time of first onset of AE, data will be summarized under the following categories:

- Weeks 1–2 (Day 1–14).
- Weeks 3–6 (Day 15–42).
- Weeks 7–10 (Day 43–70).
- Weeks 11–14 (Day 71–98).
- >14 weeks (> Day 98).

The time to first onset of AE will be calculated for TEAEs as:

$$\text{Start date of AE} - \text{Date of first dose of IMP} + 1$$

If patients have multiple occurrences of an AE then the AE will be counted once for the first occurrence only. Percentages will be based on the number of patients in the safety analysis set who have a visit or follow-up call within each time period above.

For the summary of TEAEs by time to AE resolution, data will be summarized under the following categories:

- 1 week ( $\leq 7$  days).
- 2 weeks (8–14 days).
- 3 weeks (15–21 days).
- 4 weeks (22–28 days).
- >4 weeks (>28 days).
- Ongoing (for AEs not resolved).

The time to AE resolution will be calculated for TEAEs as:

$$\text{Stop date of AE} - \text{Start date of AE} + 1$$

If patients have multiple occurrences of an AE then the AE will be counted once for the occurrence with the longest time to AE resolution. However, if any of the AEs are not resolved then the AE will be counted once within the 'Ongoing' category.

The start and stop day of the AE relative to the first dose of IMP (as recorded on the CRF) will be calculated as per Section 5.1.2. For partial dates, if it is clear from the partial date that the start/stop day was prior to the first dose of IMP, then 'pre' will be listed, similarly if it is clear that the event was post the first dose of IMP then 'post' will be listed as the start/stop day as appropriate.

All AEs will be listed. Listings will include the start and stop day of the AE, a flag for treatment emergence, and limited demographic information about the patient (age, sex, race and weight at screening). A separate listing will be provided for pre-treatment AEs, serious AEs and events of special interest (see [Appendix 1](#)).

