## 12.5 Causality Assessment

Causality assessment is required for all AEs and SAEs. Causality assessment must only be assigned by the investigator. All cases judged as having a reasonable suspected causal relationship to the IMP must be reported as such. The expression "*reasonable causal relationship*" is meant to convey in general that there are facts (evidence) or arguments to suggest a causal relationship.

The following question which must be answered by the investigator for all AEs is used to capture the reasonable causal relationship of an event to the IMP:

*"In your opinion is there a plausible relationship to the IMP?"* The answer is "yes", or "no".

Events that start before the first dose of IMP (pre-treatment) should be considered as not causally related. Where a pre-treatment event worsens in severity following the first dose of IMP a new event record should be entered into the CRF.

Considering the explanation given above, investigators are strongly encouraged to express their opinion on what the cause of an AE might be. For individual patients, the

investigator is usually in the best position to assess the underlying suspected cause of an AE. For all AEs and especially SAEs, it is important that the investigator assess not only the possible role of the IMP but also competing etiological factors as the underlying cause. Factors for consideration may include:

- Medical history.
- Lack of efficacy/worsening of treated condition.
- Concomitant or previous treatment.
- Withdrawal of IMP.
- Protocol-related procedure.

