## 12.6 Reporting Procedures for All Adverse Events

All AEs\* (including SAEs) occurring during the study will be reported on the running logs in the AE section of the CRF. This includes all events from the time following screening (Visit 1) to post study follow-up (Visit 10), whether or not attributed to IMP and observed by the investigator or patient.

\*For the patient's expected seizure types, these do not routinely require documentation as AEs. However, any worsening, including change in the pattern or severity of seizures, must be documented as an AE. Any AE which meets SAE criteria should still be reported as a SAE.

The following information will need to be provided for all AEs:

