## **D) Severity**

When describing the severity of an AE the terms mild, moderate, or severe should be used. Clinical judgment should be used when determining which severity applies to any AE.

If the severity of an AE fluctuates day-to-day, for example, a headache or constipation, the change in severity should not be recorded each time, instead only the worst observed severity should be recorded with AE start and stop dates relating to the overall event duration regardless of severity.

A severe AE is not the same as a SAE. For example, a patient may have severe vomiting but the event does not result in any of the SAE criteria above. Therefore it should not be classed as serious.

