#### **13.6.6.2 Adverse Events**

AEs will be coded according to the Medical Dictionary for Regulatory Activities dictionary.

A treatment emergent AE is one that started, or worsened in severity or seriousness, following the first dose of IMP.

Descriptive presentations of treatment emergent AEs will be given by preferred term and system organ class for the safety analysis. The number of patients reporting at least one AE will be provided.

The following summaries will be produced:

- All-causality AEs.
- Treatment related AEs.
- All-causality AEs by severity.
- All-causality serious AEs.
- Treatment related serious AEs.

- AEs reported as leading to permanent cessation of study treatment.
- Fatal AEs.

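### SAP 5.6.2 drops the protocol's worsening limb from the treatment-emergent definition, so a baseline-onset AE that becomes serious on treatment at unchanged severity can be tabulated as pre-treatment

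*SAP*

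**What the plan says.** The two documents define the same term differently. Protocol 13.6.6.2: "A treatment emergent AE is one that started, or worsened in severity or seriousness, following the first dose of IMP". SAP 5.6.2: "A treatment emergent AE (TEAE) is defined as an AE with a start date on or after the first dose of IMP". The SAP adds two refinements. An unclear partial start date defaults to treatment emergent. An event starting on the day of first dose and "marked on the CRF as “Prior to study medication” then the AE will not be considered treatment emergent". Neither deals with worsening. SAP 5.8, which records departures from the protocol, does not mention the definition.

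Three site instructions in the protocol bear on how a worsening event reaches the database:

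- Section 12.5 asks for a second record when severity rises: "Where a pre-treatment event worsens in severity following the first dose of IMP a new event record should be entered into the CRF".
- Section 12.5 also fixes causality for early-onset events: "Events that start before the first dose of IMP (pre-treatment) should be considered as not causally related".
- Section 12.6 D, on severity that varies from day to day, asks for one record: "instead only the worst observed severity should be recorded with AE start and stop dates relating to the overall event duration regardless of severity".

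Under protocol 12.6, AEs are recorded from screening (Visit 1) onward, so events with onset before first dose are in the database.

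**The concern.** The SAP's TEAE flag decides whether an event enters the by-arm safety tables or the pre-treatment summary (Table 11.11). If the flag looks only at onset, an event that the protocol treats as emergent because it became serious on treatment is filed with baseline events. The tables at stake are the all-causality TEAE tables, above all serious TEAEs.

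The change is also undeclared. Protocol section 13 requires the study report to describe deviations from the final SAP. A protocol-to-SAP change that is missing from 5.8 could therefore pass unreported.

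The omission is out of step with the rest of the SAP. The liver criteria in 5.6.3.1 count a threshold as emergent if it was not met at baseline and was met later. The C-SSRS summaries in 5.6.4.4 have an explicit category for worsening ideation.

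**Working it through.** The plan gives no figure for this point, so the check applies both definitions, together with the recording rules, to each possible AE history.

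| AE history | Protocol 13.6.6.2 | SAP 5.6.2 |
|---|---|---|
| (a) Onset on or after first dose | TEAE | TEAE |
| (b) Baseline onset, no worsening | Not a TEAE | Not a TEAE |
| (c) Baseline onset, severity rises on treatment | TEAE | TEAE if the 12.5 record is opened and dated from the worsening; otherwise missed |
| (d) Baseline onset, becomes serious and severity rises | TEAE, serious | As (c) |
| (e) Baseline onset, becomes serious, severity unchanged | TEAE, serious | Not a TEAE; goes to the pre-treatment summary |

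**Why (e) is a distinct case.** Section 12.6 D separates the two attributes: "A severe AE is not the same as a SAE". Hospital admission makes an AE serious (protocol 12.2) whatever its grade. The new-record rule in 12.5 is triggered by severity only, so a moderate event that leads to admission and stays moderate generates no new record.

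**What (c) and (d) depend on.** Section 12.5 does not say that the new record starts on the date of worsening. Nor do 12.5 and 12.6 D say which applies when a fluctuating event spans first dose.

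**Tables affected.** In case (e) the event drops out of Tables 12.1 and 12.12 (serious TEAEs, by patient and by event) and the general TEAE tables. Where the facts apply, it also drops out of 12.3 (discontinuation), 12.5, 12.7 and 12.9 (dose reduction) and 12.11 (fatal). The event should still appear in the pre-treatment AE listing (11.2) and the SAE listing (12).

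**Size.**

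- Exposure window: Visit 1 to first dose, 28 (+3) days, so 28 to 31 days.
- Planned arm: 186 × 2/6 = 62 for each active dose, and 62 for pooled placebo.
- One missed patient: 1/62 = 1.6 percentage points.
- In a placebo column split by dosing volume: 186 × 1/6 = 31, and 1/31 = 3.2 percentage points.
- The documents give no rate for such events. As an assumption only, if 0% to 3% of patients were affected, 0 to 0.03 × 62 = 1.9, or 0 to 2 patients per arm. That range includes severity cases that 12.5 should already capture, so case (e) alone would sit toward its lower end.

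The safety-set decisions in SAP 5.2.1 (one patient excluded, four reassigned to the higher dose groups) shift these denominators slightly.

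**The case against.** The case for leaving the text alone is substantial.

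- **Severity is mostly handled.** If sites follow 12.5 and date the record from the worsening, cases (c) and (d) meet the SAP's start-date rule. This stands.
- **Older conditions are not at risk.** Protocol 12.1.1 makes worsening of a pre-existing condition an AE in itself, and 12.6 does the same for worsening seizures. A reader might infer that the SAP rule hides a drug that aggravates existing disease. The documents do not support that: only events first arising between Visit 1 and first dose are exposed.
- **Eligibility narrows the window.** Exclusion 6.2.2 bars clinically relevant symptoms or significant illness in the four weeks before screening or randomization, so a significant baseline infection should usually prevent entry. Epilepsy is exempt, however. An AE of worsening seizures that starts in baseline and leads to admission on treatment remains possible. SAP 5.5.3.2.6 does count patients with epilepsy admissions separately for the baseline and treatment periods.
- **Section 12.6 D is limited to day-to-day fluctuation.** A reader might infer that it forces one record for every event that spans first dose. It does not; 12.5 is the specific rule for pre-treatment events. What stands is only that the two are not cross-referenced.
- **Treatment-related tables.** A reader might infer that these lose events through the SAP wording. A single record with pre-dose onset is already to be judged unrelated under 12.5, so it would normally stay out of Tables 12.2, 12.4, 12.6, 12.8, 12.10 and 12.13 under either definition.
- **Nothing vanishes.** SAP 5.3 orders listings by site and treatment, and 5.6.2 lists every AE with an emergence flag, with SAEs listed separately. For a handful of patients the arm can be read off.

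These points limit the consequence. None restores the missing limb or covers case (e).

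**Conclusion.** The mismatch is real and undeclared. Followed as written, SAP 5.6.2 misclassifies, against the protocol's own definition, an AE that begins between Visit 1 and first dose and becomes serious on treatment at the same severity grade. Worsening in severity is misclassified only if the 12.5 record is not opened or is not dated from the worsening.

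The stronger reading, that every baseline-onset event that becomes serious on treatment is tabulated as pre-treatment, does not hold, because many such events also rise in severity and should receive a new record.

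The number of affected events cannot be calculated from the documents and is probably small. Each missed patient is about 1.6 percentage points on the planned 62, with the all-causality tables affected and the listings intact. The correction is worth making because it repairs a stated rule behind the by-arm safety tables at almost no cost.

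**What to change.** 1. In SAP 5.6.2, restore the protocol definition: an AE with onset before first dose is treatment emergent if its severity or seriousness worsened on or after first dose.
2. Before unblinding, identify candidates from SAE data and from AE records with a pre-dose start date whose IMP action is reduced, interrupted or stopped, or whose outcome is death. Such actions can only follow dosing, but they do not by themselves prove worsening, so each record needs blinded review. The documents do not show whether the SAE form captures the date an event became serious; where it does not, that review should settle the timing.
3. If the sponsor keeps the SAP definition, declare and justify it in SAP 5.8.
4. Reconcile protocol 12.5 and 12.6 D on when one record is kept for an event that spans first dose, and state that a new record starts on the date of worsening. The blinded data review was held on 21 September 2018 (SAP 5.2.3), so this can do little for records already made; the SAP change is the effective one.

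The cost is one SAP sentence, one derivation and a short blinded review. The downside is that a few more events are counted as TEAEs.

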--	--

	
99±3). At Visits 4, 6 and 8 / the Withdrawal visit, blood samples will be taken prior to administration of IMP for measurement of concomitant AED plasma concentrations, provided the risk/benefit outcome is favorable in the investigator's opinion. Patients will be instructed to record the dosing time of their concomitant AEDs in the diary. Adherence to the titration regimen and compliance will be assessed for safety reasons. Additional safety assessments will be made by telephone at Visit 5 (Day 43±3) and at Visit 7 (Day 71±3). During these calls, patients or their caregivers will be asked for information regarding AEs, epilepsy-related hospitalizations, concomitant medications and/or changes to their medication (including AEDs).
 
Visit 8 is the 'End of Treatment'/Withdrawal visit. Patients will have blood samples collected for measurement of concomitant AED plasma concentrations (all patients, provided the risk/benefit outcome is favorable in the investigator's opinion) and PK analyses of CBD, and its major metabolites (only patients who weigh <math>\geq 20</math> kg) at the same time intervals as Visit 2. Patients (<math>\geq 20</math> kg in weight) will have blood samples collected for measurement of THC and its major metabolites in plasma at a single time point only (two to three hours after dosing). Patients will also be asked to provide a urine sample for the measurement of CBD, THC, and their major metabolites (complete void) at the time of the first blood sample and the exact urine volume recorded. Patients will be instructed to record the dosing time of their concomitant AEDs in the diary and to record their meal times the day before and the day of Visit 2 and Visit 8. Samples will be taken for determination of THC levels, IGF-1 levels and pregnancy (if appropriate). The Caregiver Impression of IMP Palatability, CGIC, CGICSD, effects on menstruation cycles (for females) and Tanner Staging (for patients aged 10–17 [inclusive], or earlier if clinically indicated by onset of menarche or other signs of precocious puberty) will also be assessed. At participating sites the Cognitive Assessment Battery will be repeated at this time (ideally before any other study procedures but can be completed on a separate day, if necessary, within three days of the visit).
 
At Visit 8, patients who have completed all of the scheduled study visits will be offered the option to enter an OLE study. Entry is to be on the same day as Visit 8 (Day 99) or within seven days of Visit 8. Patients not entering the OLE study at this visit will commence a taper period (down-titrating 10% per day for 10 days), and additional IMP will be dispensed, if required. Patients who withdraw early should also begin the taper period following the Withdrawal visit (unless continued dosing is not possible due to an AE). The IVRS will generate the patient's daily IMP dosing volumes for the 10-day

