### **9.2.7 Visit 7 (Day 71, Safety Telephone Call)**

This visit will occur 70 days after randomization (Visit 2). A visit window of  $\pm 3$  days from the scheduled visit date is permitted, but it is preferred that the visit is performed on the scheduled visit day where possible.

Visit 7 will be completed by telephone. Patients or their caregivers will be asked for information on AEs, epilepsy-related hospitalizations, concomitant medications and/or changes to medication (including AEDs).

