### **9.2.8 Visit 8 (Day 99, End of Treatment/Withdrawal Visit)**

This visit will occur 98 days after randomization (Visit 2) or earlier if the patient withdraws from the study. A visit window of  $\pm 3$  days from the scheduled visit date is permitted, but it is preferred that the visit is performed on the scheduled visit day where possible. Patients will be instructed to record the dosing time of their concomitant AEDs in the diary. They will also be asked to record their meal times the day before and the day of Visit 8.

The following assessments will be made at Visit 8 / the Withdrawal visit: vital signs, physical examination (including height and body weight), ECG, EDSS, Sleep Disruption 0–10 NRS, CGIC, CGICSD, QOLCE, C-SSRS (Children's Since Last Visit), cognitive assessment battery (at participating sites), details of menstruation (for females), Tanner Staging (for patients aged 10–17 [inclusive], or earlier if clinically indicated by onset of menarche or other signs of precocious puberty) and the Vineland-II. The Caregiver Impression of IMP Palatability will also be assessed. Clinical laboratory samples (blood and urine [where possible]) will be taken for hematology, biochemistry, urinalysis, a urine THC screen (required), determination of serum IGF-1 levels and a pregnancy test (using a serum sample, as appropriate). The patient's IVRS report and paper diary will

be reviewed and the information recorded along with information regarding AEs, epilepsy-related hospitalizations, concomitant medications and/or changes to medication (including AEDs). The investigator must assess adherence to the dosing regimen.

Prior to the final dose of maintenance IMP, blood samples will be taken to determine plasma concentrations of CBD and its major metabolites (only patients who weigh  $\geq 20$  kg) and, provided the risk/benefit outcome is favorable in the investigator's opinion, concomitant AEDs (all patients). The final maintenance dose of IMP will then be taken in the clinic. ECG and vital signs will be re-assessed two to three hours post-dose. Further blood samples will be taken for CBD PK analyses. The presence of THC in plasma will also be assessed at a single time point (two to three hours post-dose). A urine sample will be collected (complete void) at the time of first blood sample collection for both CBD and THC analysis, and the exact urine volume will be recorded. See [Section 9.1.10](#).

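### SAP 5.6.2: the Weeks 11–14 percentage for time of first AE onset can drop compliant, fully exposed patients from the denominator while still counting their events

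*SAP*

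**What the plan says.** SAP 5.6.2 divides first onset into five intervals: Days 1–14, 15–42, 43–70, then "Weeks 11–14 (Day 71–98") and ">14 weeks (> Day 98"). Time to onset runs from the first dose to the AE start date. If an AE recurs, "the AE will be counted once for the first occurrence only". Percentages are based on "patients in the safety analysis set who have a visit or follow-up call within each time period above". Nothing limits the numerator to patients who meet that condition.

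AEs are collected continuously. Protocol 12.6 says of AE reporting: "This includes all events from the time following screening (Visit 1) to post study follow-up (Visit 10"), whether or not a visit falls near the event.

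Two scheduled contacts border the Weeks 11–14 interval. For Visit 7, a telephone call, Protocol 9.2.7 says "This visit will occur 70 days after randomization (Visit 2"), and the synopsis gives "Visit 7 (Day 71±3"). For Visit 8, Protocol 9.2.8 says "This visit will occur 98 days after randomization (Visit 2) or earlier if the patient withdraws from the study", again with a window of ±3 days. For both visits the protocol prefers the scheduled day where possible.

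**The concern.** The denominator rule appears meant to remove patients who are no longer observed. It uses a contact inside the interval as a stand-in for being under observation, and that works only if every observed patient is certain to have such a contact. In Days 71–98 the two candidate contacts sit on the edges of the interval, and each may fall outside it. A patient who keeps every window and takes IMP throughout can then be missing from the denominator, while an AE that starts in the interval and is reported at Visit 8 enters the numerator.

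At stake is the percentage for the last full interval on treatment, in a table meant to show how first onset changes over time. That percentage would be built differently from the three before it, and in one direction only.

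**Working it through.** **Inputs.** Intervals and denominator rule: SAP 5.6.2. Visit days and windows: Protocol 9.2.2 to 9.2.8 and Appendix 1. Day 1 is the date of Visit 2 (SAP 5.1.2, on-site first dose). The plan gives no figure on this point, so there is none to reproduce.

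**Step 1: which contacts are certain to fall in each interval, with windows kept?**

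| Interval | Certain | Possible |
|---|---|---|
| Days 1–14 | Visit 2 (Day 1) | Visit 3 (12–18) |
| Days 15–42 | Visit 4 (26–32) | Visits 3, 5 (40–46) |
| Days 43–70 | Visit 6 (54–60) | Visits 5, 7 |
| Days 71–98 | none | Visit 7 (68–74), Visit 8 (96–102) |

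The weekly safety calls (Protocol 9.2.11) do not fill the gap. They run from Visit 9 or final dosing, so they do not reach a patient still on treatment.

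**Step 2: which visit dates leave Days 71–98 empty?** Visit 7 must be on Days 68–70 (3 of 7 days) and Visit 8 on Days 99–102 (4 of 7 days). That is 3 × 4 = 12 of the 7 × 7 = 49 in-window pairs.

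**Step 3: direction.** A patient with a contact in the interval was still under observation on its first day. The SAP denominator is therefore a subset of the patients at risk, while the numerator is unchanged. If a share q of at-risk patients is excluded, the percentage is multiplied by 1/(1 − q), which is never below 1.

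**Step 4: size, under stated assumptions.** Suppose a share s of visits is held exactly on the scheduled day, the rest are spread evenly over the other 6 window days, and Visits 7 and 8 are independent. Then:

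- P(Visit 7 on Days 68–70) = 3(1 − s)/6 = (1 − s)/2
- P(Visit 8 on Days 99–102) = s + 3(1 − s)/6 = (1 + s)/2
- q = (1 − s)(1 + s)/4 = (1 − s²)/4

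The last two columns take 62 patients in a group (186 × 2/6), ignore withdrawals, and assume 5 patients with a first onset in the interval. With everyone at risk in the denominator, the percentage is 5/62 = 8.1%.

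| s | q | 1/(1 − q) | Expected denominator | Percentage |
|---|---|---|---|---|
| 1/7 (uniform) | 12/49 = 24.5% | 1.32 | 46.8 | 10.7% |
| 0.5 | 18.8% | 1.23 | 50.4 | 9.9% |
| 0.7 | 12.8% | 1.15 | 54.1 | 9.2% |
| 0.9 | 4.8% | 1.05 | 59.1 | 8.5% |
| 1 | 0% | 1.00 | 62 | 8.1% |

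The values of s and the 5 events are illustrative.

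**Step 5: when is the share zero?** It is zero if every Visit 7 is on Day 71 or later, or if every Visit 8 is by Day 98. It is also zero if each patient's two visits shift by the same number of days d. The visits are scheduled 28 days apart (99 − 71) and the interval is 28 days long (98 − 71 + 1). With d from −3 to −1, Visit 8 falls on Days 96–98; with d from 0 to +3, Visit 7 falls on Days 71–74. Exclusion needs a gap of at least 99 − 70 = 29 days.

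**The case against.** The best defence is that the rule is a workable proxy in one descriptive table and that its effect may be small. Much of this stands.

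- **Visit dates are unlikely to be uniform or independent.** The protocol prefers the scheduled day, and Visit 7's scheduled day lies inside the interval. A family that keeps the same weekday for both contacts is never excluded. A reader might take 24.5% or 1.32-fold as the expected effect or as an upper bound. It is neither: it is the result of one model, and the documents contain no visit dates with which to choose a model.
- **Zero exclusion is not a special case of perfect timing.** A reader might infer that the problem vanishes only if every visit is on its nominal day. Step 5 shows three broader conditions.
- **The table still carries the time pattern.** A reader might infer that it cannot show whether onset falls off over time. SAP 5.1 has counts presented alongside percentages, and the AE listings give start days. Only one interval's percentages are affected.
- **No bias between arms is shown.** The rule is the same in every arm of a double-blind trial, and nothing in the documents suggests that visit timing differs by treatment.
- **Other contacts could help.** The SAP does not say that unscheduled visits are excluded, and these could bring some patients back.

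None of this removes the defect. The rule still makes a treated patient's place in the denominator depend on whether a call came on Day 70 or Day 71, and it does not apply the same condition to the numerator.

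**Conclusion.** The rule is wrong as written for Days 71–98. It can exclude compliant patients who were on treatment for the whole interval while their AEs stay in the numerator, and it can only raise the Weeks 11–14 percentage in Table 11.6. Assuming independent visits, the inflation is 1.05-fold with 90% of visits on the scheduled day, 1.15-fold with 70%, and 1.32-fold with uniform timing; it is 1.00 under the conditions in Step 5. Where the trial lies in that range depends on actual visit dates. Overall AE incidence and all efficacy analyses are untouched. This is a minor point: a percentage in one safety table that should be defined correctly, and no threat to the trial's conclusions.

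**What to change.** Replace the denominator sentence in SAP 5.6.2 with one along these lines: *percentages for each interval use the safety-set patients who are on treatment or still under AE follow-up on the first day of that interval, derived from dosing and last-contact dates.* Apply it to every interval, so that all the percentages in the table are built the same way.

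The cost is one sentence and one changed derivation, from dates already collected. If the data are already unblinded, make the change and report it as a deviation from the SAP in the clinical study report, as Protocol 13 requires.
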